### **Safety Assessment:**

Safety will be assessed by physical examinations, Eastern Cooperative Oncology Group (ECOG) criteria for performance status, laboratory tests, adverse events, and concomitant medication usage. The following adverse events (including laboratory abnormalities reported as adverse events) that occur between the first dose of either study drug through 30 days after the last dose of either study drug will be collected:

- Treatment-emergent serious adverse events
- Grade  $\geq 3$  adverse events
- Adverse events of special interest, and any adverse event resulting in ibrutinib or daratumumab dose interruption, reduction or discontinuation

Any laboratory assessments associated with the above adverse events should be collected in the CRF. The severity of adverse events will be assessed using National Cancer Institute Common Terminology Criteria for Adverse Events Version 4.03.

Schema

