#### **6.1.5. Clinical Studies-Ibrutinib**

In WM, 2 pivotal trials have been completed and reported. In 2015, Treon et al reported on the initial efficacy in a Phase II study enrolling 63 rituximab refractory WM subjects . In this report the median serum IgM level decreased from 3520mg/dL to 880 mg/dL at time of best response. An overall response rate (ORR) 90.5% with major responses defined as, partial response (PR), very good partial response (VGPR) or complete response (CR), of 73%. Mutational genotypes were associated with responses with mutated *MYD88* L265P only subjects with 91.2% achieving a major response. Subjects with mutated *MYD88* and mutated *CXCR4* had a major response rate of 61.9% and those with wt sequences had a major response rate of only 28.6%. At 24 months the estimated rate of PFS was 69.1% and the OS was estimated at 95.2%

Safety analysis revealed 15% of patients experienced grade 3 or greater neutropenia, 13% experienced grade 3 or greater thrombocytopenia. Grade 3 or greater nonhematologic toxicity was rare with the vast majority of toxicities considered Grade 2 or less. The most common Grade 2 toxicities were related to gastrointestinal disorders and infections with up to 6% of patients experiencing grade 2 reflux or pneumonias. Grade 2 or greater atrial fibrillation was noted in 5% of patients with only 2% of patients experiencing post procedural bleeding.

In 2017, the iNNOVATE investigators published a sub study analysis reporting on the efficacy and safety of single agent ibrutinib in relapsed refractory WM patients. The study is a currently ongoing international randomized Phase 3 study accruing patients with relapsed rituximab refractory disease. The study randomized patients to 3 arms; rituximab plus ibrutinib, rituximab plus placebo, or ibrutinib alone. The published data focused on the results from the ibrutinib only

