## **20. Procedures for Reporting Safety Data and Product Quality Complaints for Janssen Medicinal Products to Janssen Scientific Affairs, LLC**

All adverse events and special situations, whether serious or non-serious, related or not related, following exposure to a Janssen medicinal product are to be documented by the investigator and recorded in the CRF and in the subject's source records. Investigators must record in the CRF their opinion concerning the relationship of the adverse event to a Janssen medicinal product.

All (serious and non-serious) adverse events reported for a Janssen medicinal product should be followed-up in accordance with clinical practice.

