## **20.2. Non-Serious AEs**

All non-serious adverse events should be reported to Janssen Scientific Affairs, LLC according to the timeframe outlined in the Research Funding Agreement section entitled Reporting of Data.

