- Type, severity, frequency, duration, and relationship to study drug of any AEs or abnormalities of laboratory tests, SAEs, or AEs leading to discontinuation will be recorded.
- Monthly IgM serum levels and every 6 month CT scans will be recorded and used to assess efficacy.
- Subjects may be discontinued at any time at the discretion of the Investigator. The following may be justifiable reasons for the Investigator to remove a subject from the study:
  - Non-compliance
  - Withdrawal of consent by the subject
  - Erroneous inclusion into the study
  - Development of defined exclusion criteria
  - Intolerable toxicity or adverse event
  - Pregnancy
  - Termination of the study by the sponsor

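### The synopsis limits adverse event collection to serious, Grade ≥3, special-interest and dose-changing events, the body of the protocol requires all events, and nothing says which rule governs

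*Combined protocol and SAP*

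**What the plan says.** The two rules, both in current text:

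- **Synopsis, Safety Assessment.** Collection is defined by "The following adverse events (including laboratory abnormalities reported as adverse events) that occur between the first dose of either study drug", with a window that closes 30 days after the last dose of either drug. The list then has "Treatment-emergent serious adverse events", Grade ≥3 events, and events of special interest together with "any adverse event resulting in ibrutinib or daratumumab dose interruption, reduction or discontinuation". It has no catch-all category.
- **Section 20.** The events to be documented in the case report form (CRF) and source records are "All adverse events and special situations, whether serious or non-serious, related or not related". There is no grade threshold and no time window.
- **Section 20.2.** "All non-serious adverse events should be reported to Janssen Scientific Affairs, LLC", on a timetable set in the funding agreement.
- **Section 19.** The principal investigator provides every event, serious or not, in report format.
- **Section 22.** The items to be recorded include "Type, severity, frequency, duration, and relationship to study drug of any AEs".
- **Section 15.1.** REDCap is to hold all toxicity and adverse event data for every enrolled patient.

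Section 1.1 sets safety and toxicity of the combination as the primary objective, with no grade limit. Section 16 bases the precision of the primary endpoint on non-hematologic Grade ≥3 events.

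**The concern.** A coordinator who works from the synopsis and one who works from Section 20 would record different events for the same patient. They would differ only on low-grade events, and there the synopsis rule can lose information.

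Those events matter here. Section 6.1.5, in a sentence on non-hematologic toxicity with ibrutinib alone, describes "the vast majority of toxicities considered Grade 2 or less". The same section reports Grade 2 reflux or pneumonia in up to 6% of patients and Grade 2 or greater atrial fibrillation in 5%. Section 6.2.5 says daratumumab had not been studied clinically in this disease. The any-grade profile is therefore a substantial part of what a 24-patient trial with a safety objective can contribute.

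**Working it through.** **1. Which events differ between the rules.** An event is collected under Section 20 but not under the synopsis only if it meets all four conditions: non-serious, Grade 1–2, not of special interest, and no effect on dosing.

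**2. Whether the special-interest category closes the gap.** Only in part.
- Section 17.3 starts infusion reactions at Grade 3, and infections and cytopenias at Grade 4. Hepatitis B reactivation, visual disturbance and other malignancies have no threshold.
- Section 17.4 covers major hemorrhage, intracranial hemorrhage of any grade, and other malignancies. Major hemorrhage means Grade ≥3 or bleeding with specified consequences, such as hospitalization or a transfusion of at least 2 units.
- Neither list includes arrhythmia, infection below Grade 4, or minor bleeding.

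**3. Whether the dose-changing category closes the gap.** Again only in part.
- The holds in Section 12.4 generally start at Grade 3 for non-hematologic toxicity, so most Grade 1–2 events would not enter this way. Febrile neutropenia of any grade would.
- Sections 12.2 and 12.2.1 have the infusion paused for a Grade 1–2 infusion-related event. On a natural reading that is a dose interruption, so low-grade infusion reactions are probably collected under both rules. The synopsis does not define the term.
- An arrhythmia that leads to therapeutic anticoagulation would bring an ibrutinib hold under Section 10.2.1 and so be collected. One that does not could be missed.

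What remains is mainly low-grade infection, minor bleeding, arrhythmia without a hold, and similar events.

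**4. Whether the planned primary estimate is touched.** The plan's own figure reproduces. Inputs from Section 16: n = 12 per cohort, proportion 15%, exact 95% interval, so x = 0.15 × 12 = 1.8.
- Lower limit: 2.5% quantile of Beta(x, n − x + 1) = Beta(1.8, 11.2), which is 1.57%.
- Upper limit: 97.5% quantile of Beta(x + 1, n − x) = Beta(2.8, 10.2), which is 46.54%.
- Width: 44.97%. The plan states 1.6% to 46.5%, width about 45.0%.

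Observed counts must be whole: 1/12 gives 0.2% to 38.5%, and 2/12 gives 2.1% to 48.4%. Both rules collect every Grade ≥3 event, so the choice of rule changes neither x nor n.

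**5. Whether the stopping rule is touched.** Section 22 counts Grade ≥3 toxicity that leads to a hold of more than 28 days or to discontinuation of either drug. Both rules collect these events, so the count out of the first 12 subjects is the same.

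**6. The window.** Only the synopsis states one for collection: first dose of either drug to 30 days after the last dose of either drug. Section 9.3.5 brings subjects who stop early back 28 days later, and Section 11.1 follows them for 28 days after removal from study. If removal falls on the day of the last dose, 30 − 28 = 2 days of the window lie beyond the last visit. For subjects who finish, the end-of-treatment visit is Cycle 37 Day 1, and Table 1 schedules none after it.

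**The case against.** The strongest reply is that the synopsis is the outlier. Several body sections require complete collection, and Table 1 has adverse events evaluated continuously and at each visit. The trial uses one REDCap database and a coordinating center, so a common CRF may settle the matter for every site. No analysis in Section 16 is an any-grade rate. All of this is fair and limits the consequence. It does not remove the contradiction: the CRF is not in the documents, and it could have been built to either rule.

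A reader might go further in three ways that the documents do not support.

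- **That collection will vary by site.** It could, but this depends on how the CRF is built. A form built to the synopsis would instead lose low-grade events everywhere.
- **That any-grade rates would be halved.** If a share f of patients is followed under the synopsis rule and a fraction c of the event is still captured there, the reported rate is the true rate × [1 − f(1 − c)]. With an assumed true rate of 40% and c = 0, f = 25%, 50% or 75% gives 30%, 20% or 10%. With f = 50% and c = 25% it gives 25%. The true rate, f and c are all assumptions, so these figures only restate them.
- **That low-grade infusion reactions would be lost.** They are probably collected as dose interruptions, so they are a weak example.

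**Conclusion.** The contradiction is real and should be resolved, but it is a limited one. Non-serious Grade 1–2 events that are not of special interest and change no dosing could be missed if the synopsis is followed, and any-grade rates could then be biased low. The direction follows from the text. The amount cannot be estimated from the documents.

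The non-hematologic Grade ≥3 proportion, its interval and the stopping rule stand as they are. That rests on reading the toxicity proportion in Section 16 as the non-hematologic Grade ≥3 proportion, the only event that section names for it. What is at risk is the descriptive low-grade profile under the primary objective, not the primary estimate or the decision to stop.

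**What to change.** - In the synopsis, replace the list with the Section 20 rule: all adverse events, all grades, recorded in the CRF. Check that the REDCap form matches.
- State the synopsis window once, in Section 20, which has none: first dose of either drug to 30 days after the last dose of either drug. Reconcile it with the 28-day visit in Section 9.3.5 and the 28-day follow-up in Section 11.1.
- Leave the 24-hour reporting rules in Sections 17.3, 17.4 and 20.1 unchanged. The synopsis list should not be kept as an expedited-reporting list. It would bring in every Grade ≥3 and dose-changing event, whereas Section 20.1 confines 24-hour transmission to serious events, events of special interest and special situations, and Section 20.2 puts non-serious events on another timetable.

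The cost is a few lines of wording and slightly more data entry for 24 patients. It is best done before data collection, because low-grade events not recorded at the time may not be fully recoverable later.

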## 1. Study Objectives

Ibrutinib is an effective treatment strategy for Waldenström's macroglobulinemia (WM) achieving major response rates of approximately 70% in rituximab refractory patients. Unfortunately these responses are generally partial responses (PR) and rapid elevations of IgM occur when the drug is held. This suggests an inability of ibrutinib to address the source of the disease. It is not yet clear whether long-term health risks of persistently elevated IgMs exist and thus we hypothesize we can deepen response rates and increase durability by adding daratumumab to ibrutinib in both treatment naïve and previously treated WM patients who have achieved a disease response plateau on ibrutinib.

We propose a multi-center, two cohort, Phase II clinical trial to investigate the effectiveness of adding daratumumab to ibrutinib in WM patients. Subjects in Cohort A will be identified by their treating physician and eligible for enrollment if they are treatment naïve or relapsed after 1 prior therapy but remain naïve to ibrutinib or BTK inhibitors and appropriate for ibrutinib based treatment. Subjects in Cohort B will be identified by their treating physician and eligible for enrollment if they have had at least 6 months of exposure to single agent ibrutinib and demonstrate an IgM response plateau defined by two IgM measurements, at least 8 weeks apart that have changed <15% from the previous mark. Enrolled subjects will be prescribed commercial ibrutinib, 420mg PO daily. The investigational agent, daratumumab will be administered based on FDA approved dosing in multiple myeloma (16mg/kg) with 8 weekly induction treatments, followed by every other week dosing for cycles 3-6, then monthly dosing, cycle 7-24. Cycle 25 and beyond subjects will continue on single agent ibrutinib. Patients will be premedicated with 100mg of methylprednisolone, 650mg of acetaminophen and 25-50mg IV of diphenhydramine 30 minutes prior to all infusions of daratumumab. Methylprednisolone dosing may be reduced to 60mg with subsequent doses after the first infusion. Subjects will be asked to take 20mg of methylprednisolone for two days after each infusion which can be eliminated after the first cycle at the discretion of the investigator.

Study visits and response assessments with IgM measurements will occur day 1 of each cycle through cycle 13 then day of 1 every three cycles after the first year on treatment. Subjects with measurable extramedullary disease will have CT scans every 6 months while on study or until radiographic CR at which point they will occur at the discretion of the investigator. Patients will be considered evaluable for response if they completed the initial 8 weeks of daratumumab induction therapy. Response assessment in Cohort B will be measured from the IgM level recorded prior to ibrutinib initiation. Subjects will continue on combination therapy for 2 years until disease progression or unacceptable toxicities at which point patients will stop daratumumab therapy and come off study. All subjects will be followed for 1 year after completing combination therapy unless they come off study early for other reasons. Subjects achieving a CR will be given an option to continue with single agent commercial ibrutinib or stop all therapy.

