**Methodology:**

We propose a multi-center, two cohort Phase II clinical trial to investigate the effectiveness of adding daratumumab to ibrutinib in WM patients. Cohort A will consist of patients who are ibrutinib naïve and appropriate for ibrutinib based treatment. Cohort B will consist of patients who have achieved a response plateau less than a complete remission (CR) on single agent ibrutinib.

Subjects in Cohort A will be identified by their treating physician and eligible for enrollment if they are treatment naïve or ibrutinib naïve after prior therapy and eligible for ibrutinib based treatment. Subjects in Cohort B will be identified by their treating physician and eligible for enrollment if they have had at least 6 months of exposure to single agent ibrutinib and demonstrate an IgM response plateau defined by two IgM measurements, at least 8 weeks apart that have changed <15% from the previous mark. In Cohort B response assessment will be measured from initial IgM level prior to ibrutinib initiation. Enrolled subjects will be prescribed commercial ibrutinib, 420mg PO daily. The investigational agent, daratumumab will be administered based on FDA approved dosing in multiple myeloma (16mg/kg) with 8 weekly induction treatments during Cycles 1 and 2, followed by every other week dosing for Cycles 3-6, then monthly dosing from Cycle 7 until Cycle 24 at which point they will continue with ibrutinib as monotherapy until Cycle 52 (4 years total) which is the predefined study completion for enrolled subjects at which point they will complete follow-up.

Study visits and response assessments with IgM measurements will occur with each cycle for the first year then every three cycles after cycle 13. Subjects with measurable extramedullary disease will have CT scans every 6 cycles until radiographic CR. Patients will be considered evaluable for response if they completed the initial 8 weeks of daratumumab induction therapy and evaluable for toxicity if receiving one dose of daratumumab. Patients will continue on combination therapy for 2 years or until disease progression or unacceptable toxicities at which point patients will come off trial. Patients achieving a CR after two years of combination therapy will be given an option to continue with single agent commercial ibrutinib.

Subjects to be enrolled	24 total subjects, 12 in Cohort A and 12 in Cohort B
Study Duration	6 years
Accrual period	2 years

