### **Evaluation of Efficacy and Safety**

Response will be assessed by the investigator, based on laboratory values, physical examinations, CT scans (or MRI if CT scan is medically contraindicated), bone marrow examinations.

All measurable disease must be documented at screening by physical examination, laboratory testing, CT scan (or MRI if CT is medically contraindicated), and bone marrow. During the study, each study visit by a physical examination and laboratory testing. Clinical disease assessments will take place at baseline, monthly for the first 12 months and then every 3 months until disease progression, death or study removal for any other reason. Additional radiographic studies will be performed every 6 months on study for patients with baseline extramedullary disease. For consistency, the same method of imaging should be performed for a subject throughout the study.

[figure not shown]

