## **9. Study Procedures**

Eligible subjects will be identified by the treating investigator and be recommended for the study based on potential to meet eligibility criteria. Identified subjects will be brought to clinic to initiate the informed consenting process. Once a subject agrees to participate they will be provided an informed consent form detailing the study design, investigational agents, risks, benefits and subject and investigator responsibilities prior to obtaining their signature.

Once consented, subjects will enter the screening phase which will last up to 28 days, during which time confirmation of eligibility and baseline evaluations will take place. Subjects meeting eligibility will then be assigned to one of two cohorts depending on their treatment history. Cohort A subjects will be ibrutinib naïve patients and cohort B will be subjects currently on ibrutinib who have reached a response plateau. Twelve patients will be enrolled into each cohort.

Subjects will then enter the treatment phase with initial induction followed by the maintenance

phase as defined by the protocol. Subjects will be followed by clinical exams, laboratory investigations and imaging until disease progression unacceptable toxicity or completion of 2 years of therapy. After completion of combination therapy, subjects will be followed for an additional year on single agent ibrutinib.

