#### **9.3.5. End of Treatment or Progression**

Subjects that complete 3 years of therapy will then come off study. At C37D1, subjects will have EOT procedures collected. Additionally any subject that comes off for therapy early for toxicity, or progression will be required to return 28 days later for EOT procedures.

EOT (to be done at Cycle 37 or at time of treatment discontinuation)

- Medical history
- Concurrent medications
- Physical exam
- Vital signs (including height and weight)
- CBC with differential
- Serum chemistry (CMP, LDH, phosphorus)
- Immunoglobulin M
- **Research** bone marrow biopsy/aspirate (at time of progression (1 green top and 1 lavender top))
- Peripheral blood research tubes C37D1 (2 lavender top tubes)
- Adverse event evaluation
- Radiographic evaluation (**Cycle 31 day 1 only [+ a 15 day window]**)

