#### **11.1. Duration of Follow Up**

The anticipated duration of patients on study will be 3 years. Patients will be followed for 1 year after completion of combination treatment, or for 28 days after removal from study, or until death, whichever occurs first. Patients removed from study for unacceptable adverse events will be followed until resolution or stabilization of the adverse event even if that period is longer than 28 days.

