#### 14.2. Time to Event Definitions

**Duration of Response (DoR):** The duration of overall response is measured from the time measurement criteria are met for Minor response or better until the first date that recurrent or progressive disease is objectively documented (taking as reference for progressive disease the smallest IgM measurements recorded since the treatment started).

**Progression-Free Survival (PFS):** PFS is defined as the duration of time from start of treatment to time of progression or death.

**Overall Survival (OS):** OS is defined as the duration of time from start of treatment to time of death or last follow-up.

**Time to Progression (TTP):** TTP is defined as the time to tumor progression as defined in Section 9.1. If the subject has not progressed, then data will be censored at the last study visit at which a tumor assessment was performed.

**Evaluation of toxicity.** All patients will be evaluable for toxicity from the time of their first treatment with Daratumumab.

**Evaluation of response.** All patients included in the study will be assessed for response to treatment if they have completed Cycle 2.

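### Disease assessment ends 28 days after a toxicity exit, so later progressions and deaths needed for PFS are not collected and the Kaplan-Meier curve is open to informative censoring

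*Combined protocol and SAP*

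**What the plan says.** **Leaving the study.** Section 1 takes patients off study at "unacceptable toxicities at which point patients will stop daratumumab therapy and come off study". The synopsis (Methodology) has the same rule: treatment runs "until disease progression or unacceptable toxicities at which point patients will come off trial".

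**End of assessment.** Section 9: "Subjects will be followed by clinical exams, laboratory investigations and imaging until disease progression unacceptable toxicity or completion of 2 years of therapy". The synopsis (Evaluation of Efficacy and Safety) schedules disease assessment after the first year "every 3 months until disease progression, death or study removal for any other reason".

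**After removal.** Section 9.3.5: "any subject that comes off for therapy early for toxicity, or progression will be required to return 28 days later for EOT procedures". That visit includes an IgM level. Section 11.1 follows patients for one year after combination treatment, "or for 28 days after removal from study, or until death, whichever occurs first". The one extension is for patients removed for unacceptable adverse events, who "will be followed until resolution or stabilization of the adverse event even if that period is longer than 28 days". It concerns the event and mentions no disease assessment.

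**Endpoints and analysis.** Section 14.2: "PFS is defined as the duration of time from start of treatment to time of progression or death". It gives a censoring rule for TTP (the last visit with a tumor assessment) and none for PFS or DoR. Section 16 plans Kaplan-Meier for PFS and OS in each cohort, if follow-up is adequate, and descriptive reporting of DoR and TTP. It names no sensitivity analysis for toxicity exits.

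**The concern.** The PFS definition does not depend on treatment status, but the conduct rules stop collecting the events it needs once a patient leaves for toxicity. Kaplan-Meier treats a censored patient as having the same future risk as those still observed. A toxicity exit is related to treatment, so that assumption is doubtful.

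The protocol supplies one reason to expect a difference. Section 3 reports that IgM climbs quickly when ibrutinib is interrupted, and that the patient stays at risk while the malignant clone persists. Section 14.1 also requires a repeat measurement before an IgM rise alone counts as progression. No visit follows the 28-day one, so a rise first seen there has no scheduled confirmation.

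Durability beyond that seen historically with ibrutinib alone is part of the Section 3 hypothesis, and the trial is offered as a platform for later studies. If the curve mainly describes patients who tolerated the combination, later planning could rest on too favorable a figure. OS has the same gap: Section 17.4 refers to survival follow-up after progression, but no such follow-up is scheduled.

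**Working it through.** **The plan's own figures.** The plan gives no precision or event figure for PFS, TTP or DoR. Its one computed figure, the interval for the toxicity proportion, reproduces as 1.57% to 46.54% (Clopper-Pearson, n = 12, count 0.15 × 12 = 1.8). It has no bearing on this point.

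**Inputs from the documents**
- 2-year PFS on ibrutinib alone: 69.1% (Sections 2 and 3).
- Stops for adverse events on ibrutinib alone: 2 of 31 = 6.5%, at a median follow-up of 18.1 months (Section 6.1.5).
- 12 patients per cohort.

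**Assumptions, not in the documents**
- Constant on-treatment hazard.
- Stop rates of 10% and 20%, spread evenly over months 0 to 12.
- Hazard ratio *h* after stopping, relative to on treatment.
- Censoring about 28 days after stopping.

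**Step 1. PFS if everyone is followed.** The monthly hazard is λ = −ln(0.691)/24 = 0.0154. For patients assigned to stop at a time *u* uniform on 0 to 12 months, 24-month PFS is

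0.691^h × [exp(12λ(h−1)) − 1] / [12λ(h−1)], with 12λ = 0.1848.

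- h = 2: 0.4775 × 1.098 = 0.524
- h = 4: 0.2280 × 1.336 = 0.305

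Mixing with the patients who do not stop:
- 20%, h = 2: 0.8 × 0.691 + 0.2 × 0.524 = 0.658
- 20%, h = 4: 0.553 + 0.2 × 0.305 = 0.614
- 10%, h = 2: 0.9 × 0.691 + 0.1 × 0.524 = 0.674
- 10%, h = 4: 0.622 + 0.1 × 0.305 = 0.652

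**Step 2. What Kaplan-Meier reports.** Simulation of large cohorts gives values just under 69.1%, because only the 28 days after stopping show the raised hazard. For the 10% and 20% rows, the fully followed PFS agrees with step 1 within simulation error. The 2/31 rows come from a separate simulation in which stops occur at a constant rate.

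| Stop rate | h | Kaplan-Meier, 24 months | All followed | Gap (points) |
|---|---|---|---|---|
| 2/31 | 2 | 69.0% | 68.1% | +0.9 |
| 2/31 | 3 | 69.0% | 67.4% | +1.6 |
| 2/31 | 5 | 68.7% | 66.3% | +2.5 |
| 10% | 2 | 69.0% | 67.4% | +1.6 |
| 10% | 4 | 68.9% | 65.3% | +3.6 |
| 20% | 2 | 68.8% | 65.7% | +3.1 |
| 20% | 4 | 68.5% | 61.4% | +7.1 |

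Gaps were taken before rounding. At 2/31 a ratio of 4 lies between +1.6 and +2.5, so about 2 points. At h = 1 there is no gap. At h = 0.5 and 2/31 the gap is −0.6. Calibrating instead to the 86% PFS at 18 months in Section 6.1.5 gives +0.6, +1.1 and +2.0 at 2/31 for h = 2, 3 and 5.

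**Step 3. Scale in a cohort of 12.** Suppose one patient is censored early and in fact progresses. The other 11 set the estimate S, while the true proportion is 11S/12. The gap is S/12 = 0.69/12 = 5.8 points. The standard error is √(0.69 × 0.31/12) = 0.134, about 13 points.

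**The case against.** The strongest reply is that direction and size are not in the documents. No post-stop hazard is given, and the IgM rebound in Section 3 concerns ibrutinib. A patient who stops only daratumumab and stays on commercial ibrutinib is outside that argument. Section 3 also attributes the rebound mainly to released IgM secretion, and Section 14.1 lets the investigator discount a rise due to a drug hold during active therapy. This stands: for daratumumab-only stops the direction is open.

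The 10% and 20% stop rates have no source, and the one documented rate gives a small bias. That also stands, although 2 of 31 comes from ibrutinib alone and the combination may differ.

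A reader might infer that PFS, TTP and DoR are all shown to be inflated. The documents do not support that. Censoring is written down only for TTP, Kaplan-Meier is planned only for PFS and OS, and the calculation above covers PFS alone.

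A reader might also infer that deaths in these patients are lost by design. Section 11.1 follows the adverse event to resolution or stabilization, Section 20.1 follows unresolved serious events, and Section 17.7 makes any death a serious adverse event. Deaths from the toxicity itself would largely be captured; later deaths would not.

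The exit rule itself is not fully settled. Sections 12.2.2 and 12.4.2 discontinue one drug without mentioning removal from study, and Section 9.3.5 places the end-of-treatment visit both at discontinuation and 28 days after it. None of these sections restores disease assessment after a toxicity exit.

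Finally, these are secondary endpoints in a descriptive pilot, no test against historical PFS is planned, and the documents do not say how the historical studies handled toxicity exits. Bias in that comparison is therefore not established.

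**Conclusion.** The gap between endpoint and follow-up is real: progressions and deaths after the 28-day visit, which the PFS definition needs, are not collected for patients who stop for toxicity. Informative censoring of the Kaplan-Meier PFS curve is therefore possible. It probably flatters the curve for patients who stop ibrutinib and could go either way for those who stop only daratumumab.

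The size depends on the assumed hazard ratio and, apart from 2 of 31, on assumed stop rates. For ratios of 2 to 4 the range runs from about 1 to about 7 points at 24 months. In most scenarios this is small beside the sampling error of a 12-patient cohort. The primary safety conclusion does not change. The case for acting is that the loss is systematic, analysis cannot recover data never collected, and the remedy is inexpensive. It is a worthwhile improvement, not a flaw that undermines the trial.

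**What to change.** In the synopsis and Sections 1, 9, 9.3.5 and 11.1, separate 'off treatment' from 'off study'. Patients who stop one or both drugs without progression would keep the already scheduled IgM and disease assessments, and have survival status recorded, until progression, new anti-WM therapy, death, withdrawal of consent or the planned study end.

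In Section 14.2, add censoring rules for PFS and DoR, and state that stopping treatment for toxicity is not a censoring event for PFS, TTP or DoR.

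Reconcile Sections 1, 9, 9.3.5, 11.1, 12.2.2, 12.4.2 and 17.4 on whether stopping one drug ends study participation, on the timing of the end-of-treatment visit, and on survival follow-up. What treatment these patients receive stays with their physicians.

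The cost is protocol wording and some extra data collection for perhaps 1 to 3 patients per cohort (10% to 20% of 12 is 1.2 to 2.4).
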